After completing the 52-week double-blind, placebo-controlled treatment period, participants will enter the post-treatment period and complete a follow-up visit 4 weeks after Visit 15/Week 52. Post-treatment follow-up telephone contacts will be performed for all participants at Weeks 60 and 64.

AEs will be monitored throughout the study and graded in severity according to the guidelines outlined in the NCI CTCAE, Version 5.0 (see Section 10.14). Regular safety assessments will be performed during the study (see Section 8.3).

Specific procedures to be performed during the study, as well as their prescribed times and associated visit windows, are outlined in the SoA in Section 1.3. Details of each procedure are provided in Section 8.

There will be a non-binding IA performed once ≥ 25 participants per group have been randomized and have completed an MRI-PDFP at the 24-week post-randomization assessment. The IA will include a review of MRI-PDFP and safety data. Results of the IA will be reviewed by an eDMC, who will make a recommendation to continue, modify, or end the study according to the plan to be described in detail in the eDMC charter.

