Note: NCI CTCAE, Version 5.0 will not be used for grading AE severity for participants known to have hypertension or with a baseline blood pressure >120 mm Hg (systolic) or >80 mm Hg (diastolic) before randomization. Instead, the investigator will assess AE intensity according to the following modified CTCAE grading:

- Grade 1: Persistent increase from baseline of 10 mm Hg to 19 mm Hg (systolic blood pressure) and/or 5 mm Hg to 9 mm Hg (diastolic blood pressure) despite continuation of any anti-hypertensive regimen being used at baseline.
- Grade 2: Persistent increase from baseline of ≥ 20 mm Hg (systolic blood pressure) and/or ≥ 10 mm Hg (diastolic blood pressure) despite continuation of any anti-hypertensive regimen being used at baseline **AND** initiation and/or dose increase of ≤ 2 anti-hypertensive agents required for management.*
- Grade 3: Persistent increase from baseline of ≥ 20 mm Hg (systolic blood pressure) and/or ≥ 10 mm Hg (diastolic blood pressure) despite continuation of any anti-hypertensive regimen being used at baseline **AND** initiation and/or dose increase of >2 anti-hypertensive agents required for management.*
- Grade 4: Life-threatening consequences (eg, malignant hypertension, transient or permanent neurologic deficit, hypertensive crisis); urgent intervention indicated.
- Grade 5: Death related to AE.

***Note:** Multiple changes made to a single medication (eg, initiation at lower dose followed by dose increase) counts as only one adjustment.

Laboratory Abnormalities

6. The participant has a CTCAE Grade 3 laboratory abnormality considered drug-related by the investigator, if clinically significant medical intervention is required to treat the event **and/or** the abnormality leads to hospitalization.
7. The participant has any CTCAE Grade 4 laboratory abnormality that requires clinically significant medical intervention to treat the event **and/or** the abnormality leads to hospitalization. Continuation/resumption of study medication may be considered if the investigator and Sponsor concur that the abnormality is **clearly not** causally related to study medication and that this does not place the participant at unnecessary risk.

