9.6.2 Analysis Methods for Safety Analyses

Safety and tolerability will be assessed by clinical review of all relevant parameters including AEs, laboratory tests, body weight, and vital signs.

Adverse Events

AEs will be coded using the standard MedDRA and grouped according to SOC.

The analysis of safety results will follow a tiered approach (Table 7). The tiers differ with respect to the analyses that will be performed.

Tier 1 Events

The safety profile of MK-3655 is not understood sufficiently to prespecify any Tier 1 events.

Tier 2 Events

Tier 2 parameters will be assessed via point estimates with 95% CIs provided for between-treatment differences in the proportion of participants with events.

Membership in Tier 2 requires that at least 4 participants in any treatment group exhibit the event; all other AEs and PDLCs will belong to Tier 3. The threshold of at least 4 events was chosen because the 95% CI for the between-group difference in percent incidence will always include zero when the treatment groups each have fewer than 4 events and thus would add little to the interpretation of potentially meaningful differences. Because many 95% CIs may be provided without adjustment for multiplicity, the CIs should be regarded as a helpful

descriptive measure to be used in review, not a formal method for assessing the statistical significance of the between-group differences in AEs and PDLs.

In addition, summary measures of AEs consisting of the percentage of participants with any AE, with a drug-related AE, with an SAE, with an AE which is both drug-related and serious, who discontinued due to an AE, and who died will be considered Tier 2 endpoints.

The 95% CIs will be provided for between-treatment differences in the percentage of participants with each Tier 2 event; these analyses will be performed using the M&N method [Miettinen, O. and Nurminen, M. 1985].

Weight change from baseline will also be considered a Tier 2 endpoint. This analysis will be performed using a cLDA model as described for LFC in Section 9.6.1.2.

Tier 3 Events

Safety endpoints that are not Tier 2 events will be considered Tier 3 events. Only point estimates by treatment group will be provided for Tier 3 safety parameters.

Continuous Safety Measures

For continuous measures such as changes from baseline in laboratory and vital signs parameters, summary statistics for baseline, on treatment, and change from baseline values will be provided by treatment group.

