10.3.5 Recording AE and SAE

AE and SAE recording

- When an AE/SAE occurs, it is the responsibility of the investigator to review all documentation (eg, hospital progress notes, laboratory, and diagnostics reports) related to the event.
- The investigator will record all relevant AE/SAE information on the AE CRFs/worksheets at each examination.
- It is not acceptable for the investigator to send photocopies of the participant's medical records to the Sponsor in lieu of completion of the AE CRF page.
- There may be instances when copies of medical records for certain cases are requested by the Sponsor. In this case, all participant identifiers, with the exception of the participant number, will be blinded on the copies of the medical records before submission to the Sponsor.
- The investigator will attempt to establish a diagnosis of the event based on signs, symptoms, and/or other clinical information. In such cases, the diagnosis (not the individual signs/symptoms) will be documented as the AE/SAE.

Assessment of intensity

- An event is defined as "serious" when it meets at least 1 of the predefined outcomes as described in the definition of an SAE, not when it is rated as severe.
- The investigator will make an assessment of intensity for each AE and SAE (and other reportable safety event) according to the NCI CTCAE, Version 5.0. Any AE that changes CTCAE Grade over the course of a given episode will have each change of grade recorded on the AE CRFs/worksheets.
 - Grade 1: Mild; asymptomatic or mild symptoms; clinical or diagnostic observations only; intervention not indicated.

- Grade 2: Moderate; minimal, local, or noninvasive intervention indicated; limiting age-appropriate instrumental activities of daily living.
- Grade 3: Severe or medically significant but not immediately life-threatening; hospitalization or prolongation of hospitalization indicated; disabling; limiting self-care activities of daily living.
- Grade 4: Life-threatening consequences; urgent intervention indicated.
- Grade 5: Death related to AE.

Assessment of causality

- Did the Sponsor's product cause the AE?

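### CTCAE grade is recorded for every AE and every grade change, but no planned AE measure is defined by grade, so severity is compared with placebo only indirectly

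*Combined protocol and SAP*

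**What the plan says.** **Collection.** Section 4.1 states: "AEs will be monitored throughout the study and graded in severity according to the guidelines outlined in the NCI CTCAE, Version 5.0". Sections 4.2.1.3 and 8.3.12 repeat the grading requirement. Section 10.3.5 has the investigator "make an assessment of intensity for each AE and SAE (and other reportable safety event) according to the NCI CTCAE", and adds: "Any AE that changes CTCAE Grade over the course of a given episode will have each change of grade recorded". The same section separates severity from seriousness: an event is serious because of its outcome, not because it was rated severe.

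**Exception.** For blood pressure, Section 7.1 says "NCI CTCAE, Version 5.0 will not be used for grading AE severity for participants known to have hypertension" or with raised baseline values. For them, "the investigator will assess AE intensity according to the following modified CTCAE grading", which still runs from Grade 1 to Grade 5.

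**Analysis.** In Section 9.6.2 the Tier 2 set includes "summary measures of AEs consisting of the percentage of participants with any AE, with a drug-related AE, with an SAE", then AEs both serious and drug-related, and finally participants "who discontinued due to an AE, and who died will be considered Tier 2 endpoints". For specific events the rule is a count: "Membership in Tier 2 requires that at least 4 participants in any treatment group exhibit the event". Tier 2 measures get a between-group difference with a 95% CI. Anything else falls to Tier 3, with by-group point estimates only. Table 7 lists the same measures and adds weight change, abuse-potential AEs and adjudicated events. Grade does not appear in either tier.

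**The concern.** Safety and tolerability compared with placebo is a primary objective (Section 3), with AEs as an endpoint. In the planned tables a Grade 1 event and a Grade 3 event of the same term count alike. Two arms could therefore show the same any-AE percentage while one carries more severe events, and no row would be built to show it.

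The SAE row is not a substitute, because the protocol defines seriousness apart from severity. The sponsor's own Phase 1 summary (Section 2.2.2.2) describes most AEs as mild or moderate. The plan for this trial contains no analysis that would support or qualify the same statement by treatment group.

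**Working it through.** **1. Which rows could carry grade.** The AE rows in Table 7, checked against Sections 7.1 and 10.3:

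| Row | Link to grade |
|---|---|
| Any AE; drug-related AE; specific AEs and SOCs | None; all grades count alike |
| SAE; serious and drug-related AE | Partial; Grade 4 (life-threatening) and some Grade 3 (hospitalization, disability) overlap the seriousness criteria |
| Discontinuation due to AE | Partial; criterion 4 (drug-related Grade 3 clinical AE) and criterion 5 (Grade 4 clinical AE unless clearly unrelated) require discontinuation |
| Death | Grade 5 |

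**2. What those links leave out.**

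- Non-serious Grade 3 clinical AEs that the investigator judges not drug-related: criterion 4 does not apply. Drug effects that investigators do not attribute to drug are a main reason for a randomized comparison.
- Non-serious Grade 3 events after the last dose. The last dose is at Week 48 (Section 4.3.3) and AEs are reported through Week 64 (Section 8.4.1), so for 64 - 48 = 16 weeks an event cannot lead to stopping study intervention.
- Grade 3 laboratory AEs outside criterion 6, which needs drug-relatedness plus either clinically significant intervention or hospitalization.
- Shifts from Grade 1 to Grade 2.

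The discontinuation row also includes stops made on other grounds, such as the weight, cortisol and IGF-1 rules or investigator discretion (Section 7.1). It cannot be read as a severity measure.

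**3. Reproducing the plan's own figures.** Inputs: n = 82 per group and the count pairs in Table 9 (Section 9.9.2). The Miettinen-Nurminen interval is the set of differences d for which |z(d)| ≤ 1.96, where

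z(d) = (p1 - p2 - d) / sqrt{ [r1(1 - r1)/n + r2(1 - r2)/n] × 2n/(2n - 1) }

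and r1, r2 are the maximum-likelihood proportions subject to r1 - r2 = d. At d = 0 both equal the pooled proportion.

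| Counts of 82 | Difference (points) | 95% CI | z(0) |
|---|---|---|---|
| 7 v 1 | 7.3 | 0.9 to 15.6 | 2.17 |
| 10 v 3 | 8.5 | 0.3 to 17.9 | 2.02 |
| 15 v 6 | 11.0 | 0.8 to 21.7 | 2.10 |

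All three exclude zero. One event fewer on MK-3655 (6 v 1, 9 v 3, 14 v 6) includes zero. Table 9 is reproduced, with those pairs as the minimum counts.

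**4. Illustration.** The documents give no Grade 3 or higher rates, so these counts are assumptions.

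- Any AE, 62 v 62: difference 0.0 points, 95% CI -13.2 to 13.2. This is what the existing row would show.
- Grade 3 or higher, 13 v 4: difference 9/82 = 11.0 points. Pooled proportion 17/164 = 0.1037; standard error at d = 0 is sqrt(0.1037 × 0.8963 × 2/82 × 164/163) = 0.0478; z(0) = 0.1098/0.0478 = 2.30. The 95% CI is 1.8 to 21.1.
- Grade 3 or higher, 10 v 3: 8.5 points, 0.3 to 17.9. This pair of counts is in Table 9, but Table 9 concerns AE incidence in general, not Grade 3 or higher events.

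**5. What a new row could detect.** Probability that its CI excludes zero with the higher rate on MK-3655, by exact binomial enumeration for assumed true rates at 82 per group: 22% for 10% v 5%; 59% for 15% v 5%; 86% for 20% v 5%; 43% for 20% v 10%; 73% for 25% v 10%. The row is informative for large differences and weak for small ones.

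**The case against.** A reader might infer that no safety measure uses grade at all, so that a shift from mild to severe events gets no between-group estimate. The documents do not support that. Section 7.1 requires discontinuation for drug-related Grade 3 clinical AEs, and for Grade 4 clinical AEs unless clearly unrelated. Discontinuation due to AE is itself a named primary safety endpoint with a Tier 2 interval. The blood-pressure exception reaches the same row, since its stopping rule matches modified Grade 3. Death carries Grade 5, and SAE overlaps Grade 4 and part of Grade 3. Weight change, the clearest Phase 1 signal, has its own Tier 2 estimate, and laboratory changes enter Tier 2 as predefined limits of change once 4 participants in a group have them. All of this stands, and it narrows the gap to the categories listed above.

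It can also be said that a by-grade summary would fall under Tier 3, where the difference is a subtraction and only the interval is missing; that Tier 2 intervals are descriptive anyway; that no endpoint names severity; and that the supplementary SAP may hold a by-grade table. The first three points limit the weight of the finding but do not remove it: Table 7 lists no grade row in Tier 3 either, and the objective is a comparison with placebo. On the last, the supplementary SAP is not available here. Section 9.6 reserves it for exploratory objectives, and Section 9.6.2 defers only adjudicated events and topics of special interest to it, not grade.

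The illustrative counts have no source in the documents. If the 13 v 4 were on-treatment, drug-related clinical events, most would already appear under discontinuation.

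**Conclusion.** The point holds in a limited form. Grade is fully collected, no AE measure is defined by it, and severity is compared with placebo only through discontinuation due to AE, SAE and death. Those rows leave identifiable classes of Grade 3 events, and all Grade 1 to Grade 2 shifts, without a between-group estimate. The data-collection instruction is sound; the gap is in Section 9.6.2 and Table 7.

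The size cannot be derived from the documents. Under the assumed counts, equal any-AE rates are compatible with an 11.0-point difference in Grade 3 or higher events whose interval excludes zero. That shows the possibility and does not predict it. This is an inexpensive improvement to a primary safety comparison, not a defect that invalidates the plan.

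**What to change.** In Section 9.6.2 and Table 7:

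- Add any AE of CTCAE Grade 3 or higher as a Tier 2 summary measure, using each participant's maximum post-randomization grade, with the Miettinen-Nurminen difference and 95% CI for each dose versus placebo.
- Tabulate specific AEs by maximum grade and treatment group, descriptively.
- Show hypertension graded on the modified Section 7.1 scale separately, since those grades are not CTCAE grades.
- Treat a drug-related Grade 3 or higher row as optional. For on-treatment clinical AEs it largely overlaps discontinuation due to AE.

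Cost: SAP wording, one Tier 2 row and one descriptive table, with no new data collection. The downside is one more interval per comparison (three in all) without multiplicity adjustment, which Section 9.6.2 already accepts for Tier 2.

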10.3.6 Reporting of AEs, SAEs, and Other Reportable Safety Events to the Sponsor

AE, SAE, and other reportable safety event reporting to Sponsor via electronic data collection tool

- The primary mechanism for reporting to the Sponsor will be the electronic data collection (EDC) tool.
 - Electronic reporting procedures can be found in the EDC data entry guidelines (or equivalent).
 - If the electronic system is unavailable for more than 24 hours, then the site will use the paper AE Reporting form.
 - Reference Section 8.4.1 for reporting time requirements.
- The site will enter the SAE data into the electronic system as soon as it becomes available.

- After the study is completed at a given site, the EDC tool will be taken off-line to prevent the entry of new data or changes to existing data.
- If a site receives a report of a new SAE from a study participant or receives updated data on a previously reported SAE after the EDC tool has been taken off-line, then the site can report this information on a paper SAE form or by telephone (see next section).
- Contacts for SAE reporting can be found in the Investigator Study File Binder (or equivalent).

SAE reporting to the Sponsor via paper CRF

- If the EDC tool is not operational, facsimile transmission or secure e-mail of the SAE paper CRF is the preferred method to transmit this information to the Sponsor.
- In rare circumstances and in the absence of facsimile equipment, notification by telephone is acceptable with a copy of the SAE data collection tool sent by overnight mail or courier service.
- Initial notification via telephone does not replace the need for the investigator to complete and sign the SAE CRF pages within the designated reporting time frames.
- Contacts and instructions for SAE reporting and paper reporting procedures can be found in the Investigator Study File Binder (or equivalent).

10.4 Appendix 4: Medical Device and Drug-device Combination Products: Product Quality Complaints/Malfunctions: Definitions, Recording, and Follow-up

Not applicable.

10.5 Appendix 5: Contraceptive Guidance

10.5.1 Definitions

Women of Childbearing Potential (WOCBP)

A woman is considered fertile following menarche and until becoming postmenopausal unless permanently sterile (see below):

If fertility is unclear (eg, amenorrhea in adolescents or athletes) and a menstrual cycle cannot be confirmed before first dose of study intervention, additional evaluation should be considered.

Women in the following categories are not considered WOCBP:

- Premenarchal
- Premenopausal female with 1 of the following:
 - Documented hysterectomy
 - Documented bilateral salpingectomy
 - Documented bilateral oophorectomy

For individuals with permanent infertility due to an alternate medical cause other than the above (eg, Mullerian agenesis, androgen insensitivity), investigator discretion should be applied to determining study entry.

Note: Documentation can come from the site personnel's review of the participant's medical records, medical examination, or medical history interview.

- Postmenopausal female
 - A postmenopausal state is defined as no menses for 12 months without an alternative medical cause.
 - A high FSH level in the postmenopausal range may be used to confirm a postmenopausal state in women not using hormonal contraception or HRT. However, in the absence of 12 months of amenorrhea, confirmation with 2 FSH measurements in the postmenopausal range is required.
 - Females on HRT and whose menopausal status is in doubt will be required to use one of the non-hormonal highly effective contraception methods if they wish to continue their HRT during the study. Otherwise, they must discontinue HRT to allow confirmation of postmenopausal status before study enrollment.

10.5.2 Contraception Requirements

Contraceptives allowed during the study include^a:

- Highly Effective Contraceptive Methods That Have Low User Dependency
Failure rate of <1% per year when used consistently and correctly.
 - Progestogen-only subdermal contraceptive implant^b
 - IUS^c
 - Non-hormonal IUD
 - Bilateral tubal occlusion
 - Azoospermic partner (vasectomized or secondary to medical cause)
This is a highly effective contraception method provided that the partner is the sole male sexual partner of the WOCBP and the absence of sperm has been confirmed. If not, an additional highly effective method of contraception should be used. A spermatogenesis cycle is approximately 90 days.

Note: Documentation of azoospermia for a male participant can come from the site personnel's review of the participant's medical records, medical examination, or medical history interview.

- Sexual Abstinence
 - Sexual abstinence is considered a highly effective method only if defined as refraining from heterosexual intercourse during the entire period of risk associated with the study intervention. The reliability of sexual abstinence needs to be evaluated in relation to the duration of the study and the preferred and usual lifestyle of the participant.

^a Contraceptive use by men or women should be consistent with local regulations regarding the use of contraceptive methods for participants of clinical studies.

^b If locally required, in accordance with CTFG guidelines, acceptable contraceptive implants are limited to those which inhibit ovulation.

^c IUS is a progestin releasing IUD.

10.6 Appendix 6: Collection and Management of Specimens for Future Biomedical Research

1. Definitions

- a. Biomarker: A biological molecule found in blood, other body fluids, or tissues that is a sign of a normal or abnormal process or of a condition or disease. A biomarker may be used to see how well the body responds to a treatment for a disease or condition.¹
- b. Pharmacogenomics: The investigation of variations of DNA and RNA characteristics as related to drug/vaccine response.²
- c. Pharmacogenetics: A subset of pharmacogenomics, pharmacogenetics is the influence of variations in DNA sequence on drug/vaccine response.²
- d. DNA: Deoxyribonucleic acid.
- e. RNA: Ribonucleic acid.

2. Scope of Future Biomedical Research^{3, 4}

The specimens consented and/or collected in this study as outlined in Section 8.10 will be used in various experiments to understand:

- The biology of how drugs/vaccines work
- Biomarkers responsible for how a drug/vaccine enters and is removed by the body
- Other pathways with which drugs/vaccines may interact
- The biology of disease

The specimen(s) may be used for future assay development and/or drug/vaccine development.

It is now well recognized that information obtained from studying and testing clinical specimens offers unique opportunities to enhance our understanding of how individuals respond to drugs/vaccines, enhance our understanding of human disease and ultimately improve public health through development of novel treatments targeted to populations with the greatest need. All specimens will be used by the Sponsor or those working for or with the Sponsor.

3. Summary of Procedures for Future Biomedical Research^{3, 4}

a. Participants for Enrollment

All participants enrolled in the clinical study will be considered for enrollment in future biomedical research.

b. Informed Consent

Informed consent for specimens (ie, DNA, RNA, protein, etc.) will be obtained during screening for protocol enrollment from all participants or legal guardians, at a study visit by the investigator or his or her designate. Informed consent for future biomedical research should be presented to the participants on the visit designated in the SoA. If delayed, present consent at next possible Participant Visit. Consent forms signed by the participant will be kept at the clinical study site under secure storage for regulatory reasons.

A template of each study site's approved informed consent will be stored in the Sponsor's clinical document repository.

c. eCRF Documentation for Future Biomedical Research Specimens

Documentation of participant consent for future biomedical research will be captured in the eCRFs. Any specimens for which such an informed consent cannot be verified will be destroyed.

d. Future Biomedical Research Specimen(s)

Collection of specimens for future biomedical research will be performed as outlined in the SoA. In general, if additional blood specimens are being collected for future biomedical research, these will usually be obtained at a time when the participant is having blood drawn for other study purposes.

4. Confidential Participant Information for Future Biomedical Research^{3,4}

In order to optimize the research that can be conducted with future biomedical research specimens, it is critical to link participants' clinical information with future test results. In fact, little or no research can be conducted without connecting the clinical study data to the specimen. The clinical data allow specific analyses to be conducted. Knowing participant characteristics like sex, age, medical history and intervention outcomes are critical to understanding clinical context of analytical results.

To maintain privacy of information collected from specimens obtained for future biomedical research, the Sponsor has developed secure policies and procedures. All specimens will be single-coded per ICH E15 guidelines as described below.

At the clinical study site, unique codes will be placed on the future biomedical research specimens. This code is a random number which does not contain any personally identifying information embedded within it. The link (or key) between participant identifiers and this unique code will be held at the study site. No personal identifiers will appear on the specimen tube.

5. Biorepository Specimen Usage^{3,4}

Specimens obtained for the Sponsor will be used for analyses using good scientific practices. Analyses utilizing the future biomedical research specimens may be performed by the Sponsor, or an additional third party (eg, a university investigator) designated by the Sponsor. The investigator conducting the analysis will follow the Sponsor's privacy and confidentiality requirements. Any contracted third party analyses will conform to the specific scope of analysis outlined in future biomedical research protocol and consent. Future biomedical research specimens remaining with the third party after specific analysis is performed will be reported to the Sponsor.

6. Withdrawal From Future Biomedical Research^{3,4}

Participants may withdraw their consent for future biomedical research and ask that their biospecimens not be used for future biomedical research. Participants may withdraw consent at any time by contacting the investigator for the main study. If medical records for the main study are still available, the investigator will contact the Sponsor using the designated mailbox ([contact]). Subsequently, the participant's specimens will be flagged in the biorepository and restricted to main study use only. If specimens were collected from study participants specifically for future biomedical research, these specimens will be removed from the biorepository and destroyed. Documentation will be sent to the investigator confirming withdrawal and/or destruction, if applicable. It is the responsibility of the investigator to inform the participant of completion of the withdrawal and/or destruction, if applicable. Any analyses in progress at the time of request for withdrawal/destruction or already performed prior to the request being received by the Sponsor will continue to be used as part of the overall research study data and results. No new analyses would be generated after the request is received.

In the event that the medical records for the main study are no longer available (eg, if the investigator is no longer required by regulatory authorities to retain the main study records) or the specimens have been completely anonymized, there will no longer be a link between the participant's personal information and their specimens. In this situation, the request for withdrawal of consent and/or destruction cannot be processed.

7. Retention of Specimens^{3,4}

Future biomedical research specimens will be stored in the biorepository for potential analysis for up to 20 years from the end of the main study. Specimens may be stored for longer if a regulatory or governmental authority has active questions that are being answered. In this special circumstance, specimens will be stored until these questions have been adequately addressed.

Specimens from the study site will be shipped to a central laboratory and then shipped to the Sponsor-designated biorepository. If a central laboratory is not utilized in a particular study, the study site will ship directly to the Sponsor-designated biorepository. The specimens will be stored under strict supervision in a limited access facility which

operates to assure the integrity of the specimens. Specimens will be destroyed according to Sponsor policies and procedures and this destruction will be documented in the biorepository database.

8. Data Security^{3,4}

Databases containing specimen information and test results are accessible only to the authorized Sponsor representatives and the designated study administrator research personnel and/or collaborators. Database user authentication is highly secure, and is accomplished using network security policies and practices based on international standards to protect against unauthorized access.

9. Reporting of Future Biomedical Research Data to Participants^{3,4}

No information obtained from exploratory laboratory studies will be reported to the participant, family, or physicians. Principle reasons not to inform or return results to the participant include: Lack of relevance to participant health, limitations of predictive capability, and concerns regarding misinterpretation.

If important research findings are discovered, the Sponsor may publish results, present results in national meetings, and make results accessible on a public website in order to rapidly report this information to doctors and participants. Participants will not be identified by name in any published reports about this study or in any other scientific publication or presentation.

10. Future Biomedical Research Study Population^{3,4}

Every effort will be made to recruit all participants diagnosed and treated on Sponsor clinical studies for future biomedical research.

11. Risks Versus Benefits of Future Biomedical Research^{3,4}

For future biomedical research, risks to the participant have been minimized and are described in the future biomedical research informed consent.

The Sponsor has developed strict security, policies, and procedures to address participant data privacy concerns. Data privacy risks are largely limited to rare situations involving possible breach of confidentiality. In this highly unlikely situation, there is risk that the information, like all medical information, may be misused.

12. Questions

Any questions related to the future biomedical research should be emailed directly to [contact].

13. References

1. National Cancer Institute [Internet]: Available from <https://www.cancer.gov/publications/dictionaries/cancer-terms?cdrid=45618>
2. International Council on Harmonisation [Internet]: E15: Definitions for Genomic Biomarkers, Pharmacogenomics, Pharmacogenetics, Genomic Data and Sample Coding Categories. Available from <http://www.ich.org/products/guidelines/efficacy/efficacy-single/article/definitions-for-genomic-biomarkers-pharmacogenomics-pharmacogenetics-genomic-data-and-sample-cod.html>
3. Industry Pharmacogenomics Working Group [Internet]: Understanding the Intent, Scope and Public Health Benefits of Exploratory Biomarker Research: A Guide for IRBs/IECs and Investigational Site Staff. Available at <http://i-pwg.org/>
4. Industry Pharmacogenomics Working Group [Internet]: Pharmacogenomics Informational Brochure for IRBs/IECs and Investigational Site Staff. Available at <http://i-pwg.org/>

